### 7.1.3 Solicited systemic reactions

[figure not shown]
Solicited systemic reactions after IM and/or ID administration are defined as AEs with the following PTs:

- Pyrexia
- Chills
- Myalgia
- Rash

occurring in the period after and up to and including 14 days after the Day 0, Day 28, and Day 112.

*Pyrexia* should be used as PT for temperatures above 38.3°C only, which is not as in the FDA guidelines presented in the protocol Appendix 1 stating temperatures above 38.0°C. For increased temperatures at or below 38.3°C, the PT *Body temperature increased* is used and thus not included as events. If the temperature is unknown, *Pyrexia* will be used, and the event included.

The number and percentage of subjects and the number of events will be presented by PT:

- At Day 0 for the four treatment regimens present
  - Cohort A-C
  - Cohort D
  - Cohort E
  - Cohort F
- At Day 28 and Day 112 for the 10 treatment regimens present
  - Cohort A1
  - Cohort A2
  - Cohort B
  - Cohort C
  - Cohort D1
  - Cohort D2
  - Cohort E1
  - Cohort E2
  - Cohort F1
  - Cohort F2

The number and percentage of subjects with events occurring in the period after and up to and including 14 days after the Day 0 vaccination and the corresponding 95% CI will be presented together with a pairwise comparison of number of subjects with events using Fishers exact test for the following:

- Cohort A-C vs Cohort D
- Cohort A-C vs Cohort E
- Cohort A-C vs Cohort F

All information will be listed.

[figure not shown]
#### 7.1.4 Any other AEs

Any other AEs are all TEAEs not included in the above three sections.

The number and percentage of subjects and the number of events will be presented by system organ class (SOC) and preferred term (PT) for the following timespans:

- From Day 0 vaccination to before Day 28 vaccination for the four treatment regimens present
  - Cohort A-C
  - Cohort D
  - Cohort E
  - Cohort F
- From Day 28 vaccination to before Day 112 vaccination and
- From Day 112 vaccination to before Day 140 vaccination

The immediate above two tables will include the nine treatment regimens present, where the placebo cohort (F) will be regarded as one

- Cohort A1
  - Cohort A2
  - Cohort B
  - Cohort C
  - Cohort D1
  - Cohort D2
  - Cohort E1
  - Cohort E2
  - Cohort F
- From Day 140 vaccination to end of trial for the 11 treatment regimens present, where the placebo cohort (F) will be regarded as one
  - Cohort A1
  - Cohort A2
  - Cohort B1
  - Cohort B2
  - Cohort C1
  - Cohort C2
  - Cohort D1
  - Cohort D2
  - Cohort E1
  - Cohort E2
  - Cohort F

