At V8 (Day 126), the diary card is collected and reviewed. The AEs and CM are recorded. Vital signs are taken, eye and symptom-directed physical examination are performed. Refer to Table 3 for eye examination method required at V8. Blood samples for safety and immunogenicity determination (please refer to type of tests in Table 4) are drawn. Ocular sample is taken.

At V9 (Day 140), the AEs and CM are recorded. Vital signs are taken. Eye and symptom-directed physical examinations are performed. Refer to Table 3 for eye examination method required at V9. Before the vaccinations, blood samples for safety and immunogenicity determination (please refer to type of tests in Table 4) are drawn, urine for pregnancy and ocular sample are taken. The subjects receive the final vaccination with a TO CTH522 (or placebo) boost as specified in the Figure 1. The subjects are observed for any immediate AE for 60 minutes after the vaccination. The diary card is issued with instructions before discharge from the site.

At V10 (Day 143), the diary card is reviewed. The AEs and CM are recorded. Vital signs are taken. Eye and symptom-directed physical examination are performed. Refer to Table 3 for eye examination method required at V10. Ocular sample is taken.

At V11 (Day 154), the diary card is collected and reviewed, AEs and CM are recorded. Vital signs are taken. Eye and symptom-directed physical examinations are performed. Refer to Table 3 for eye examination method required at V11. Blood samples for safety and immunogenicity determination (please refer to type of tests in Table 4) are drawn and ocular sample is taken.

V12 (Day 238) is the end-of-trial visit. The AEs and CM are reviewed and recorded. Vital signs are taken. Eye and physical examinations (including symptom-directed) are performed. Refer to Table 3 for eye examination method required at V12. Urine is collected for pregnancy and PCR for *C. Trachoma* and gonorrhoea infection test. Blood samples for safety and immunogenicity determination (please refer to type of tests in Table 4) are drawn and ocular sample is taken.

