8.7 Safety assessments

The trial staff must record all AEs, non-serious and serious, expected and unexpected in the relevant form of the eCRF. This starts from the time after the subject has signed the informed consent form (ICF) at V1 until the end-of-trial at V12.

The source of AEs covers, for example, the subject's response to questions about his/her health (a standard non-leading question), information from diary card, symptoms spontaneously reported by a subject, results from pre-defined laboratory testing and examinations where the findings are assessed by the investigator to be clinically significant changes or abnormalities, and other information relating to the subject's health becoming known to the investigator (for example hospitalisation).

The subjects will remain at the site for 60 minutes after each vaccination so that any immediate AEs observed may be recorded. It is also documented if no immediate AEs occurred. Trial staff will ensure that the subjects have a diary card, ruler to measure and thermometer to enable them to record AEs while away from the clinical site.

From the day of vaccination until seven days later, solicited AEs and unsolicited AEs will be recorded through the use of diary cards. Between Day 7–14, the subject will be asked to fill in details in the diary *only* if they experience an AE or if any medications were taken.

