## 7 Statistical Methodology for Primary and Secondary Endpoints

### 7.1 Analysis and Presentation of the co-Primary Safety Endpoints

The co-primary endpoints are:

- Solicited local injection site reactions after ID and/or IM administration of the vaccines: erythema, pruritus, pain, tenderness, swelling, and warmth occurring up to and including 14 days after any IMP administration
- Solicited local reactions after TO administration of the vaccine: watering eyes, swelling of eyelid, eye redness, and eye discomfort occurring up to and including 14 days after any IMP administration
- Solicited systemic reactions after IM and/or ID administration of the vaccines: oral temperature  $> 38.3^{\circ}\text{C}$ , chills, myalgia, and rash occurring up to and including 14 days after any IMP administration
- Any other adverse events (AEs)

These are collected in the subjects' diaries.

The primary analyses will be carried out for the SAF.

AEs will be coded using the Medical Dictionary for Regulatory Activities (MedDRA) version 22.1 - Sep 2019. AEs will be regarded as treatment emergent AEs (TEAEs) if they occur after administration of randomised treatment.

Only TEAEs will be summarised. The summaries will include number of events, number of subjects, and proportion of subjects reporting these events.

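### SAP 7.1.4 reports the co-primary 'any other AEs' only over between-vaccination spans of 28, 84, 28 and 98 days, so the tables cannot be read dose by dose and dilute post-dose signals after Days 28 and 140

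*SAP*

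**What the plan says.** SAP 7.1 lists any other AEs as the fourth co-primary safety endpoint. SAP 7.1.4 defines it as every treatment-emergent AE not already counted under the three solicited endpoints. It presents number and percentage of subjects and number of events, by system organ class and preferred term, for four spans:

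- "From Day 0 vaccination to before Day 28 vaccination for the four treatment regimens present"
- "From Day 28 vaccination to before Day 112 vaccination and"
- "From Day 112 vaccination to before Day 140 vaccination"
- "From Day 140 vaccination to end of trial for the 11 treatment regimens present"

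The last span closes at Day 238: "V12 (Day 238) is the end-of-trial visit" (Protocol 8.2). The three solicited endpoints in SAP 7.1.1 to 7.1.3 each use a fixed 14-day window after vaccination, and SAP 8 explains that window for those three only.

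On data collection, Protocol 8.7 says "From the day of vaccination until seven days later, solicited AEs and unsolicited AEs will be recorded through the use of diary cards". It continues "Between Day 7–14, the subject will be asked to fill in details in the diary", restricted to days with an AE or a medication. The same section requires all AEs to be recorded from consent at V1 to V12. SAP 7.1 nevertheless says of all the co-primary endpoints that they are collected in the diaries.

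**The concern.** Four tables that each start at a vaccination invite reading as AE experience after dose 1, dose 2, dose 3 and the ocular boost. Two of the spans are about three times as long as the other two, and a percentage of subjects with at least one event grows with the time observed. A change from one table to the next therefore mixes any vaccine effect with elapsed time.

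There is a second cost, within each table. Where a reaction clusters in the days after a dose, a long span adds weeks of unrelated illness to both numerator groups and shrinks the contrast between cohorts.

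This matters here for two kinds of event. Protocol 12.1 lists headache, fatigue and malaise among the related systemic reactions seen in more than one in ten subjects in the earlier trial. None is a solicited term in this SAP, so section 7.1.4 is their only display by vaccination. In addition, SAP 7.1.3 counts solicited systemic reactions only after Days 0, 28 and 112. Chills, myalgia or rash after the Day 140 ocular boost fall into the 98-day table.

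**Working it through.** **1. Span lengths.** Inputs are the visit windows in Protocol Table 3, repeated in SAP Table 1: V4 = V2 + 26–30, V7 = V4 + 77–91, V9 = V7 + 26–30, V12 = V9 + 91–105. The midpoints are 28, 84, 28 and 98. Their running sum is 28, 112, 140, 238, which reproduces the stated trial days exactly. The longest short span (30 days) is well below the shortest long span (77 days), so the two kinds never overlap within the windows.

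**2. Diary days.** The diary covers 14 days after each vaccination in every span. Its share is 14/28 = 50%, 14/84 = 16.7%, 14/28 = 50% and 14/98 = 14.3%.

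**3. Expected counts with no vaccine effect.** The documents give no background AE rate, so a constant rate is assumed; it cancels from the ratios.

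- Full capture to V12: 28 : 84 : 28 : 98 = 1 : 3 : 1 : 3.5.
- Half of events outside the diary captured (assumption): effective days = 14 + 0.5 × (span − 14) = 21, 49, 21, 56, giving 1 : 2.3 : 1 : 2.7.
- No events outside the diary captured: 14 days in every span, giving 1 : 1 : 1 : 1.

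**4. Percentage of subjects with at least one event**, 1 − exp(−rate × effective days):

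| Assumed rate per subject-day | Capture outside diary | Day 0–28 | Day 28–112 | Day 112–140 | Day 140–238 |
|---|---|---|---|---|---|
| 0.002 | full | 5.4% | 15.5% | 5.4% | 17.8% |
| 0.005 | full | 13.1% | 34.3% | 13.1% | 38.7% |
| 0.01 | full | 24.4% | 56.8% | 24.4% | 62.5% |
| 0.005 | half | 10.0% | 21.7% | 10.0% | 24.4% |
| 0.005 | none | 6.8% | 6.8% | 6.8% | 6.8% |

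**5. Dilution of a post-dose signal.** Assume a background of 0.005 per subject-day, full capture, and a rate that doubles for 14 days after a dose. Over d days the risk is 1 − exp(−0.005 × d) without the effect and 1 − exp(−0.005 × (d + 14)) with it.

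| Window | Without | With | Risk ratio |
|---|---|---|---|
| 14 days | 6.8% | 13.1% | 1.93 |
| 28 days | 13.1% | 18.9% | 1.45 |
| 84 days | 34.3% | 38.7% | 1.13 |
| 98 days | 38.7% | 42.9% | 1.11 |

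**The case against.** The strongest reply is that no planned analysis makes the comparison that span length distorts. SAP 7.1.4 contains four descriptive tables whose columns are cohorts. The safety objectives concern IM dose, added route and adjuvant, not successive vaccinations. Within a table every cohort has the same nominal span, and placebo Cohort F appears in all four. The column groupings also change (4, 9, 9 and 11), so a dose-to-dose reading takes some effort, and the span boundaries are printed. All of this stands, and it limits the harm to descriptive reading and sensitivity. It does not remove the dilution in step 5, which acts inside each table. Cohort F is a weak reference: Protocol 11.4.3 allots 9% of 66 subjects to it, about 6, so one subject moves its percentage by about 17 points.

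Two stronger readings are tempting, and the documents do not support them.

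- **That doses 2 and 4 are bound to look worse.** This is a tendency only. With 6 subjects, periods treated as independent, 0.005 per day and full capture, the second period exceeds the first with probability about 0.71, ties at 0.19 and falls below at 0.10. At 0.002 with half capture, the probability of exceeding is about 0.37. Percentages by individual preferred term would also be smaller than those for any event.
- **That unequal diary coverage drives the swing.** Diary days are 14 in every span. Their lower share in the long spans dampens the pattern, from 3 to 2.3 in step 3.

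Taken literally, the SAP 7.1 statement that the endpoints come from diaries would make the pattern vanish. But SAP 7.1.4 takes in all remaining treatment-emergent AEs and runs to end of trial, and Protocol 8.7 records AEs to V12, so events outside the diary belong in the tables.

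SAP 7.2.1 adds summaries by relationship and severity, and listings, which help separate related events from background illness. It specifies no split by vaccination.

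**Conclusion.** The point holds as a weakness of presentation and sensitivity in a co-primary safety endpoint. It is not a bias in any planned test. The span lengths are exact. The 1 : 3 : 1 : 3.5 pattern rests on an assumed constant background rate with full capture to V12 and weakens as capture outside the diary falls. The risk ratios of about 1.13 and 1.11, against 1.93 in a 14-day window, rest on the assumed rate of 0.005 and an assumed doubling for 14 days; they illustrate the loss and do not predict it. A reader might infer that the comparison of cohorts within a period is biased. It is not: it is less sensitive after the Day 28 and Day 140 doses. The remedy is cheap, so the change is worth making.

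**What to change.** In SAP 7.1.4:

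1. Add a table of any other AEs with onset within 14 days after each vaccination, the window of SAP 7.1.1 to 7.1.3, using the cohort groupings already planned for each period.
2. Show the rest of each period separately, with events per 100 subject-days based on each subject's actual days.
3. Keep the full-period tables as supportive.
4. State that AEs recorded at visits outside the diary are included, and align the data-source sentence in SAP 7.1 with Protocol 8.7.

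AE onset dates (Protocol 10.1.1) and vaccination dates suffice, so no new data, design change or additional testing is needed. The cost is SAP wording, one further split of four planned tables, and longer output.

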## 7.2 Analysis and Presentation of Other Safety Endpoints

Other safety endpoints are

- AEs
- Vital signs
- Safety laboratory data

### 7.2.1 Adverse Events

The summaries will include number of events, number of subjects, and proportion of subjects reporting these events.

Certain, probable, or possible related AEs are defined as Adverse Drug Reactions (ADRs).

An overall summary table will include summary of TEAEs, TESAEs, Fatal AEs, ADRs, AEs leading to drug withdrawal, drug interruption, or leading to withdrawal from trial, AEs by severity, AEs by relationship, AEs by outcome, and ADRs by severity.

A summary by SOC and PT will be presented for:

- TEAEs
- Serious Adverse Events (SAEs)

- TEAEs by severity (mild, moderate, severe, potentially life-threatening)
- TEAEs by relationship (Certain, probable, possible, not related)
- ADRs by severity
- TEAEs leading to drug interrupted
- TEAEs leading to drug withdrawn
- TEAEs leading to withdrawal

Listings will be made of all AEs, including non-TEAEs, SAEs, clinically significant AEs, ADRs including Suspected Unexpected Serious Adverse Reaction (SUSARs), and TEAEs leading to drug interruption or withdrawal from treatment.

### 7.2.2 Vital signs

Vital signs assessments are heart rate, oral temperature, systolic and diastolic blood pressure.

Vital signs will be summarised by visit including change from baseline. Boxplots will be presented by visit.

All data will be listed.

### 7.2.3 Laboratory Safety Data

Abnormal clinically significant laboratory should be reported as AEs, please refer to section 7.2.1 regarding the presentation of AEs.

Subject ID, visit number, collection date, reason for missed sample, and presence of abnormal and clinically significant laboratory values (yes/no) at the visit will be listed.

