8.11 Laboratory assays

Testing for *C. trachomatis* infection, gonorrhoea, syphilis, HIV, hepatitis B and C will be done at the laboratory facility at Charing Cross Hospital, which is part of ICHT.

Laboratory safety tests will be analysed at the lab facility at Hammersmith Hospital, which is also part of ICHT. Peripheral blood will be collected and analysed for the following biochemistry and haematology parameters at the timepoints specified in Table 3:

- Renal urea and electrolytes profile (sodium, potassium, chloride, urea, creatinine)
- Liver function tests (ALT, alkaline phosphatase, total bilirubin, total protein, albumin)
- Full blood count: WBC, lymphocytes, monocytes, eosinophils, neutrophils, basophils, RBC, haemoglobin, haematocrit, and platelets)

FDA guidelines on toxicity grading scale for subjects enrolled in vaccine trials will be used by the investigator for grading the intensity of AEs including lab-related AEs (Appendix 1).

A pregnancy test will be performed on-site by analysis of a urine sample for human chorionic gonadotrophin collected from female subjects at screening, the day of the vaccination and the final visit. Testing will be done at the NIHR Imperial Clinical Research Facility.

Serum IgG samples will be analysed at SSI. Other exploratory immunogenicity analysis will be analysed as specified in Table 4. Samples for PBMC isolation will be shipped on the day of collection from the investigator site to ICL, for processing and storage. The serum IgG samples will be processed and stored at the investigator site until the last sample has been collected. All samples intended to be analysed at SSI will be shipped after the last subject's last visit (LSLV) but no later than two weeks after date of LSLV. The samples must be shipped on dry ice with storage conditions monitored during the transport to SSI by use of a temperature logger. Documentation of the dispatch of samples from the investigational site and the receipt of the samples at SSI should be in accordance with the relevant SSI procedures for dispatch and receipt of samples. It is the responsibility of the site to pack the samples according to the above and arrange the transport from the site to SSI.

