11.2 Data management

CHLM-02 is run as a Electronic Data Capture (EDC) trial, i.e. relevant data are entered by the site directly into the clinical database. Electronically transferred data will be handled and managed by [REDACTED] as well as the database and application.

The eCRF is designed to capture required information in compliance with GCP standards. The eCRF system is hosted by IBM eClinical, an EDC software and services company that is EU-US Privacy Shield certified.

All data, except for immunogenicity data, will be collected using an eCRF compliant with 21 CFR Part 11 regulation. Safety laboratory data will be collected via the local laboratories and transferred to the eCRF by the trial staff at the site.

Data management will be performed in accordance with applicable standards and data cleaning procedures. Only authorised access to the eCRF will be possible using an encrypted username and password. Roles in the system are given according to functions. All tasks performed in the eCRF are logged in an audit trail.

The eCRF will contain validation checks according to the Trial Validation Plan to maintain an ongoing quality check of data entered. All data validation will be performed as part of the system.

The investigator will approve the data using an electronic signature and thereby confirm the accuracy of the data recorded.

Medical History and AEs will be coded using the pre-defined version of the Medical Dictionary for Regulatory Activities (MedDRA) concerning system organ class, high-level group term, high-level term, preferred term and lowest level term. Concomitant medication will be coded using the WHOCC-ATC/DDD, an Anatomical Therapeutic Chemical classification system and the Defined Daily Dose drug dictionary. Coding of AE and CM shall be entered into the trial database.

Further details about trial setup and closure will be documented in the Data Handling Protocol prepared by [REDACTED].

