**Table 1: Flow chart**

Trial visit (V)	1	2	3	4	5	6	7	8	9	10	11	12
Trial day	-	0	14	28	42	56	112	126	140	143	154	238
Windows (days)	-90 to -1	0	V2 + 12-16	V2 + 26-30	V4 + 12-16	V4 + 26-30	V4 + 77-91	V7 + 12-16	V7 + 26-30	V9 + 2-4	V9 + 12-16	V9 + 91-105
Informed consent	X											
Med. hist+demographics	X											
In-/exclusion criteria	X	X										
Blood for hep B and C, HIV, syphilis	X											
PCR for C. Trachoma and gonorrhoea infection 	X											X
Urinary pregnancy test	X	X		X			X		X			X
Physical examination	X											X
Eye exam including retina*	X*				X			X			X	
Eye exam**	X	X		X	X	X	X	X	X	X	X	X
Record weight/height	X											
Vital signs 	X	X	X	X	X		X	X	X	X	X	X
Concomitant medication	X	X	X	X	X	X	X	X	X	X	X	X
Randomisation		X										
Vaccination and route		1 IM		2 IM ID TO			3 IM ID TO			4 TO		
Issue diary card		X		X			X		X			
Review diary card			X		X			X		X	X	
Symptom-directed PE		X	X	X	X	X	X	X	X	X	X	X
Record adverse events	X	X	X	X	X	X	X	X	X	X	X	X
Safety lab 	X*	X*	X*	X*	X*		X*	X*	X*		X*	X*
Serum IgG ELISA 		X	X	X	X	X	X	X	X		X	X
Serum IgA ELISA+anti-CTH522 IgG subtypes + neutralising ab 		X	X	X	X	X	X	X	X		X	X
Ocular anti-CTH522 IgG + IgA ELISA (strip)		X		X	X	X	X	X	X	X	X	X
T- and B-cell Elispot frozen PBMCs 		X	X	X	X	X	X	X	X		X	X
ICS flow frozen PBMCs 		X	X	X	X	X		X	X		X	X
Transcriptional analysis frozen PBMCs 		X						X			X	
End-of-trial												X

ID=intradermal; IM=intramuscular; PE=physical examination; TO=topical ocular; V=visit

\*A biomicroscopy (e.g. via slit lamp examination), examining all areas of the eye including the retina which can be performed by a specialist at an eye clinic. If this procedure cannot be performed at V1, it is acceptable at V2 as long as it is performed prior to the first vaccination.

\*\*Eye examination not involving fundoscopy or any other examination modality that necessitates unacceptable prolonged closeness between examiner and participant or where the examination cannot be performed using standard personal protective equipment for examiner and participant.

[figure not shown]

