### 5 Planned Statistical Methods

If nothing else is stated, all tables, figures and listings will be presented by treatment group (i.e., A1, A2, B1, B2, ..., F2), and will be reported by actual received treatment for the SAF. A subject who receives more or less of the treatment than intended, will be presented in the cohort they belong to. If any subjects receive incorrect treatment, they will be presented separately.

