#### 5.1 Statistical Considerations

Baseline is defined as the last assessment with available data prior to the first administration of trial medication. Day 0 is the day of first administration with IMP. Assessments from scheduled visits will be presented when available, otherwise the first unscheduled visit succeeding the scheduled visit in question is used.

Categorical data will be summarized by treatment group, using number and percentages of subjects. For calculation of percentages the denominator will either be the number of subjects in the analysis set or the number of subjects in the analysis set with non-missing values. Continuous data will be presented using the number of subjects (n), mean, standard deviation (SD), median, minimum, and maximum if nothing else is stated. Both the absolute values and the change from baseline will be presented.

Descriptive statistics for all endpoints will be presented by treatment group and visit (if applicable) using observed cases, i.e., no imputation of missing data will be performed.

All statistical tests will be two-sided and performed on a 5 % significance level. Estimated treatment differences and 95 % confidence intervals (CI) will be presented together with the corresponding p-value.

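### Laboratory shifts and eye findings not judged clinically significant by the investigator reach no cohort-level output in the SAP

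*SAP*

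**What the plan says.** **Laboratory data.** SAP 7.2 lists safety laboratory data beside adverse events (AEs) and vital signs as other safety endpoints. SAP 7.2.3 then gives two routes. The first is the AE route: "Abnormal clinically significant laboratory should be reported as AEs, please refer to section 7.2.1 regarding the presentation of AEs". SAP 7.2.1 tabulates AEs by system organ class and preferred term, including "TEAEs by severity (mild, moderate, severe, potentially life-threatening", and SAP section 5 makes treatment group the default for every table. The second is a listing of subject, visit, collection date, reason for a missed sample, and a flag: "presence of abnormal and clinically significant laboratory values (yes/no) at the visit will be listed". The listing names no analyte and no value.

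**General rules.** For continuous data SAP 5.1 states: "Both the absolute values and the change from baseline will be presented". It also calls for descriptive statistics on all endpoints by group and visit, where applicable. Vital signs (SAP 7.2.2) get this treatment: by-visit summaries, change from baseline, boxplots and a full listing.

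**Data capture and grading.** Protocol 11.2 states: "Safety laboratory data will be collected via the local laboratories and transferred to the eCRF by the trial staff at the site". Protocol 8.11 states: "FDA guidelines on toxicity grading scale for subjects enrolled in vaccine trials will be used by the investigator for grading the intensity of AEs", including laboratory-related ones. The grades attach to AEs, not to every measured value.

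**Eye examinations.** SAP Table 1 has a row "Eye exam including retina" at V1, V5, V8 and V11, and a standard examination row at V1, V2 and V4 to V12. Sections 5 to 7 of the SAP specify no output for either.

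**Declared deviations.** SAP section 8 mentions neither subject. Its last bullet says in general terms that presentations are adapted to the data.

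**The concern.** Under protocol 8.7, a laboratory or examination finding becomes an AE only when the investigator assesses it as a clinically significant change or abnormality. That judgement is made subject by subject. A modest movement shared by most of a cohort, with each value unremarkable alone, need not trigger it in anyone. Such a pattern shows only when values are summarised by cohort and compared with baseline and placebo, which the SAP does not plan for laboratory data.

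Two features of the trial make this matter. Cohort E receives CTH522 with CAF09b, a combination that protocol section 12 says has not been given to humans before. The safety of topical ocular (TO) CTH522 is part of a primary objective, yet the solicited ocular endpoint in SAP 7.1.2 consists of four symptom terms taken from subject diaries. A retinal or slit-lamp finding without symptoms, and not judged clinically significant, has no place in the planned report.

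**Working it through.** **1. Laboratory schedule, checked against the plan's own figure.** Protocol Table 4 gives 13 ml at V1 and 8 ml at each of V2, V3, V4, V5, V7, V8, V9, V11 and V12. The sum is 13 + 9 × 8 = 85 ml, which matches protocol 8.10. That confirms ten laboratory visits. V1 is screening and V2 is drawn before the first vaccination, so 10 − 2 = 8 are post-vaccination.

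**2. Parameters** (protocol 8.11). Renal and electrolytes 5, liver 5, blood count 10: 5 + 5 + 10 = 20.

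**3. Size of the reduction**, with all 66 subjects attending every visit:
- planned post-vaccination values: 66 × 8 × 20 = 10,560
- flags in the listing for those visits: 66 × 8 = 528

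**4. Eye examinations after the first vaccination** (SAP Table 1):
- standard, V4 to V12, 9 visits: 66 × 9 = 594
- including retina, V5, V8 and V11: 66 × 3 = 198

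**5. Planned presentation, side by side:**

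| Data | AE route | By-visit summary | Change from baseline | Values listed |
|---|---|---|---|---|
| Vital signs (SAP 7.2.2) | not stated in 7.2.2 | yes | yes | yes |
| Laboratory (SAP 7.2.3) | if clinically significant | no | no | no, flag only |
| Eye examinations | if clinically significant (protocol 8.7) | no | no | no |

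**6. What Appendix 1 can grade.** It has no grades for chloride, monocytes, basophils, RBC or haematocrit, so 20 − 5 = 15 parameters can enter a grade-shift table. For haemoglobin change from baseline, the mildest grade begins at any decrease. The immunogenicity row of Table 4 sums to 92 + 80 + 80 + 80 + 80 + 50 + 92 + 80 + 92 + 80 = 806 ml. With safety samples the total is 806 + 85 = 891 ml, in line with the approximately 900 ml in protocol section 12. Mild haemoglobin shifts are therefore to be expected in every cohort, placebo included.

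**7. Group sizes.** Protocol 11.4.3 gives 91% active: 0.91 × 66 ≈ 60, leaving 6 on placebo. If the five active cohorts are equal (an assumption, since Figure 1 is not shown), each has 60 / 5 = 12.

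**8. Ocular groupings** (SAP Table 2). At Days 28 and 112, TO CTH522 is Cohort B; TO placebo is A2, D1, E1 and F1; no TO is A1, C, D2, E2 and F2. At Day 140 every group receives TO, so no untreated comparison remains afterwards, including at V11.

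**The case against.** A reader might infer that laboratory results enter the SAP only as a yes/no listing, or that cohort-level toxicity cannot be assessed at all. The documents do not support either reading. The first sentence of SAP 7.2.3 sends clinically significant abnormalities to the AE tables, which are by group and severity. Protocol 8.7 does the same for examination findings. SAP 7.1.4 tabulates other treatment-emergent AEs by regimen in four periods. SAP 7.1.2 tabulates solicited ocular reactions by cohort, with Fisher tests of B against A2 and B against F1 after Days 28 and 112. What is missing lies below the clinical-significance threshold.

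The conflict with SAP 5.1 is also softer than it first appears. Its continuous-data format gives way where something else is stated, and its by-visit rule applies where applicable. Protocol 11.4.4 plans vital-sign summaries but names no laboratory or eye-examination analysis, and neither is a primary endpoint in its own right. So 7.2.3 can be read as a deliberate exception. That stands as a reading, but the SAP gives no reason for the exception, and the closing bullet of section 8 is too general to declare it.

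Finally, protocol 11.2 does not say that numeric values are entered. The fields in the 7.2.3 listing would equally fit an eCRF page that holds only the flag. This objection stands, and it affects the cost of the fix.

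It is also tempting to size the loss by the upper confidence limit for no flagged subjects in a cohort of 12, which is 1 − 0.025^(1/12) = 26.5%. That limit follows from the cohort size and applies to any binary safety outcome. It does not measure what the listing discards.

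**Conclusion.** The point holds in a limited form. Apart from clinically significant findings reported as AEs, the SAP specifies no cohort-level summary and no listing of numeric laboratory values, and no table or listing of eye-examination results. At full attendance, up to 10,560 post-vaccination values are represented by at most 528 flags, and up to 594 standard and 198 retinal examinations have no specified output. Clinically significant toxicity remains visible by group. Smaller systematic shifts and eye findings below that judgement do not.

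This should be changed because safety is the primary objective and the measurements are already scheduled. The counts assume complete attendance by 66 subjects. Any new summaries will be descriptive: placebo has about 6 subjects, and active cohorts about 12 if equal. Whether numeric values are in the database is not established by the documents.

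**What to change.** - **Laboratory summaries.** In SAP 7.2.3, summarise each parameter by cohort and visit with absolute value and change from baseline, as 7.2.2 does for vital signs, and list the values.
- **Grade shifts.** Add a table of baseline grade against worst post-vaccination grade for the parameters that Appendix 1 grades, leaving out chloride, monocytes, basophils, RBC and haematocrit. Read haemoglobin change against placebo, because about 900 ml of blood is drawn from every subject.
- **Eye examinations.** Add a normal/abnormal table or listing for the retinal and standard examinations. Group by TO CTH522, TO placebo and no TO before the Day 140 administration, and by the Day 140 regimens in SAP Table 2 afterwards.
- **If not adopted.** Declare in SAP section 8 that laboratory values and eye-examination results are presented only through AEs and the flag listing, and say why.

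The cost is a few standard tables and listings, with no new procedures for subjects, provided that numeric values are in the eCRF as protocol 11.2 suggests. If only the flag is stored, a data transfer from the local laboratory is also needed. Availability should be confirmed first, for eye-examination results as well.
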